Additional outcomes will include: intraoperative minutes from NMBR administration to qTOF T4/T1 >0.9 , to extubation, and total in operating room time; incidence of residual NMB in PACU based on qTOF; number of events and accumulated minutes of hypoventilation in PACU; frequency of patients with ≥ 1 events of delayed postoperative hypoventilation (daily for up to 3 postoperative days) and accumulated minutes of hypoventilation; delayed recurrence of NMB based on qTOF; presence of pre-defined postoperative pulmonary complications during hospital stay and by the postoperative day 14 ± 3 ; standardized Patient-Reported Outcomes Measurement Information System (PROMIS®) dyspnea functional limitations questionnaire score compared to patient's baseline; pre-defined kidney graft outcomes; hospital resources utilization (e.g. hospital length of stay, ICU admission) and their cost estimates.

[figure not shown]
B. Description of Population to be Enrolled

We will include adults (≥ 18 years and ≤ 90) diagnosed with severe kidney dysfunction (defined by plasma creatinine clearance <30 mL/min) and planning on kidney transplantation surgery at the University of Colorado Hospital. Exclusion criteria: patients unable to sign the informed consent, pregnant women, Body Mass Index (BMI) > 40 , pre-existing oxygen or ventilatory dependency (24h use of oxygen or other noninvasive or invasive ventilatory support), or patients with any pulmonary, neuromuscular or other disease that severely limits their respiratory functional status (e.g. unable to achieve 4 Metabolic Equivalent of Tasks, METs, such as climbing up 1 flight of stairs[32]), or any contraindication for any of the study-related medications or interventions.

C. Study Design and Research Methods

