Screening for eligibility and consenting will take place once the patient has been accepted for kidney transplantation at the University of Colorado Hospital by the Transplant Surgery team. Randomization will occur after patients consent for the study. Only the PI will remain unblinded to the group allocation (see below).

Preoperative data will be collected by the blinded investigator (study coordinator), including baseline vital signs (including room air SpO₂), comorbidities, medications, and kidney graft relevant factors. The baseline dyspnea scores will be assessed by asking patients to complete the PROMIS® v1.0 Dyspnea Functional Limitations Short Form 10a_9-2-2016 questionnaire (available at http://www.healthmeasures.net/administrator/components/com_instruments/uploads/PROMIS%20SF%20v1.0-Dyspnea%20Functional%20Limitations%2010a_9-2-2016.pdf). This is a validated and standardized short questionnaire to quantitate if sugammadex used for NMBR reduces the subjective dyspnea scores relative to baseline.

Intraoperative phase

We will perform a prospective parallel randomized study of rocuronium/sugammadex (intervention) vs. rocuronium/neostigmine (control) for NMB and NMBR at the end of kidney transplantation surgery. This will be performed by the unblinded investigator, following the following protocol(s):

- A quantitative TOF (qTOF) monitor (the Stimpod NMS450®, Xavant Technology Ltd., South Africa, the acceleromyography-based monitor available at UCH, and/or the TwitchView™, Blink Device Company, Seattle, WA, an electromyography-based monitor) will guide the NMB and NMBR management in all study patients. Quantitative NMB monitoring are considered superior to the more routinely-used but subjective qualitative TOF monitors[34, 35]. The qTOF monitor will be placed in the ulnar nerve territory to stimulate the adductor pollicis muscle[36] immediately after loss of consciousness during induction of anesthesia. The exact location of monitoring will be marked and used for qTOF measurements in the postoperative period.
- NMB brief protocol: Rocuronium will be the NMB agent used in both groups as guided by the qTOF and following standard dosing protocols in order to achieve adequate NMB to allow the intubation and surgical procedure (routinely T4/T1 < T3 until closure of surgical incision). Rocuronium dosing: 0.6-1.2 mg/kg for intubation, 0.08-0.2 mg/kg bolus for maintenance with recovery of second twitch (T2) in qTOF.

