- NMBR brief protocol: The sugammadex (intervention) or neostigmine (control) will be administered at the end of the surgery. The goal will be to administer the appropriate NMBR medication when ≥ 2 twitches are objectivized with the qTOF monitor. NMBR drugs and dosing for each group will follow standard of care FDA-approved doses, as follows: Sugammadex 2 mg/kg will be administered when spontaneous recovery has reached the reappearance of the second twitch in response to TOF stimulation.

	Sugammadex dosing (mg/kg)	Neostigmine dosing (mg/kg)
T4 recovered	2	0.03-0.05 (max 5 mg)
T2/T3 recovered	2	0.05-0.07 (max 5 mg)
T0/T4 with 1-2 post-tetanic twitches present or T1 recovered	4 or wait	Wait

Overdosing of neostigmine will be avoided to prevent neostigmine-induced muscle weakness. Neostigmine will be administered simultaneously with the appropriate glycopyrrolate dose (0.2 mg per 1.0 mg of neostigmine).

Extubation will be performed following the usual standard of care criteria of adequate level of consciousness, presence of airway protection reflexes and spontaneous ventilation parameters in addition to quantitative TOF $T4/T1 >0.9$. The following times (minutes) will be recorded: NMBR administration-to-T4/T1 >0.9 , NMBR administration-to-extubation, total operating room time.

Postoperative in-hospital phase

The blinded investigator will collect the following study-related information:

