Incidence of residual or recurrent NMB in the postoperative floor. This will be calculated as described before (T4/T1 <0.9 , considered severe if T4/T1 <0.4), as an average of 3 repetitions obtained on two occasions separated by ≥ 6 h daily on postoperative days 1-3 or until the end of monitoring criteria have been met.

Morphine equivalents will be calculated from individual opioid doses administered to each patient following standard conversion formulas[21, 40]. This morphine equivalent dose will be calculated for the PACU period and daily for 3 first postoperative days or until the end of monitoring criteria have been met, and used as covariate in the logistic regression analysis.

Time from NMBR administration to quantitative TOF T4/T1 >0.9 (minutes, one decimal). The quantitative TOF will be repeated at 80 mA every 30 seconds from the moment the NMBR medication (sugammadex or neostigmine) has been completely administered intravenously.

Time from NMBR administration to extubation (minutes, once decimal).

Time of total operating room time (minutes), counting from in-room time stamp to out-of-room time stamp.

The PROMIS® v1.0 Dyspnea Functional Limitations Short Form 10a_9-2-2016 questionnaire is a validated and standardized short questionnaire to quantitate if sugammadex used for NMBR reduces the subjective dyspnea scores relative to baseline. It will be completed by the patient in the preoperative phase and during the postoperative follow up. It is available at http://www.healthmeasures.net/administrator/components/com_instruments/uploads/PROMIS%20SF%20v1.0-Dyspnea%20Functional%20Limitations%2010a_9-2-2016.pdf.

Postoperative Pulmonary Complications (PPCs) following previous definitions[13, 41, 42], including:

Respiratory Failure, defined as[41]: "When postoperative $\text{PaO}_2 < 60\text{mmHg}$ on room air, a ratio of PaO_2 to inspired oxygen fraction < 300 or arterial oxyhemoglobin saturation measured with pulse oximetry (SpO_2) $< 90\%$ and requiring oxygen therapy".

Unplanned intubation with postoperative mechanical ventilation (POMV), defined as placement of a breathing tube that was not intended or planned, excluding instances of intubation during an unplanned return to the operating room. Also excluded those patients that were transferred intubated and ventilated to the intensive care unit (ICU) from the operating room.

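### Recovery and extubation times start at dosing, but at deep block waiting is compulsory for neostigmine and optional for sugammadex, so the clock can start at different depths and waiting can be left out unequally

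*Combined protocol and SAP*

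**What the plan says.** Section III.A lists among the additional outcomes "intraoperative minutes from NMBR administration to qTOF T4/T1 >0.9 , to extubation". Section III.F (Variables/Time Points of Interest) defines them as "Time from NMBR administration to quantitative TOF T4/T1 >0.9 (minutes, one decimal") and "Time from NMBR administration to extubation (minutes, once decimal"). Both start when the reversal drug is given.

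Section III.C (Intraoperative phase, NMBR brief protocol) says when that is. The text sets one aim for both arms: "The goal will be to administer the appropriate NMBR medication when ≥ 2 twitches are objectivized with the qTOF monitor". It adds: "Sugammadex 2 mg/kg will be administered when spontaneous recovery has reached the reappearance of the second twitch in response to TOF stimulation". The table below it has a row for deeper block, "T0/T4 with 1-2 post-tetanic twitches present or T1 recovered". In that row the sugammadex column allows either 4 mg/kg or waiting, and the neostigmine column allows only waiting. In the two rows for lighter block, both drugs have a dose.

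The same section describes the block during surgery as "routinely T4/T1 < T3 until closure of surgical incision", with maintenance boluses given as the second twitch recovers.

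One other time is recorded: "Time of total operating room time (minutes), counting from in-room time stamp to out-of-room time stamp". No interval from the end of surgery to recovery or extubation is defined, and the twitch count at dosing is not a listed variable. Statistical Methods names no analysis for the times. Under Multiplicity, secondary analyses are exploratory.

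**The concern.** A time-to-event comparison between randomised arms needs a start point that treatment cannot move. Here the start point comes after randomisation, and the rule for reaching it differs by arm at one range of depths.

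Take two patients with a single twitch at the end of surgery. The sugammadex patient may be dosed, and the clock started, at once. The neostigmine patient must first recover to at least the second twitch, and those minutes are counted in neither speed outcome. The two clocks then start at different depths and at different times after surgery ended.

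These are the trial's only direct measures of speed of reversal. If enough patients are deeply blocked at closure, a reader could not tell how much of a difference, or of a lack of one, reflects drug speed and how much reflects waiting that was not counted. The choice between dosing and waiting under sugammadex is also made by an investigator who knows the allocation.

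**Working it through.** The plan gives no figure on this point to reproduce: no expected recovery times, no share of patients deeply blocked at closure and no waiting time. The check therefore sets the rules side by side and then works out what the omitted waiting could amount to.

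**Rules at the moment reversal is due (Section III.C)**

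| Depth of block | Sugammadex | Neostigmine | Can the start rule differ by arm? |
|---|---|---|---|
| Fourth twitch recovered | Dose | Dose | No |
| Second or third twitch recovered | Dose | Dose | No |
| Post-tetanic twitches only, or first twitch | Dose or wait | Wait | Yes |

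The third row can arise under the protocol, because block is maintained until the incision is closed and topped up when the second twitch returns. How often it arises is not stated.

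**Omitted waiting**

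- q = share of patients with fewer than 2 twitches when reversal is due, taken as equal in the two arms. Assumed 0.10 to 0.40.
- W = mean wait, in minutes, among patients who wait. Assumed 10 to 20.
- s = share of affected sugammadex patients dosed at once. Range 0 to 1, since the table permits either choice.

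Mean wait left out per patient:

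- Neostigmine: q × W
- Sugammadex: q × (1 − s) × W
- Difference between arms: q × W − q × (1 − s) × W = q × s × W

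| q | W (min) | s = 0 | s = 0.5 | s = 1 |
|---|---|---|---|---|
| 0.10 | 10 | 0 | 0.5 | 1 |
| 0.25 | 15 | 0 | 1.9 | 3.75 |
| 0.40 | 20 | 0 | 4 | 8 |

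The range is 0 to 8 min per patient on average. Wider assumptions widen it: q = 0.50, W = 30 and s = 1 give 0.50 × 1 × 30 = 15 min.

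**Direction.** Time from a common origin equals the wait plus the time from administration. With no other delays, the neostigmine-minus-sugammadex difference from a common origin therefore equals the difference from administration plus q × s × W. As q × s × W cannot be negative, the planned outcome can only show a smaller sugammadex advantage than the common-origin time would.

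**Depth at the start.** When s is above 0, some sugammadex clocks start at a depth at which no neostigmine clock may start. The documents give no recovery time by depth, so the effect of this on the time from administration cannot be calculated.

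**The case against.** The strongest reply is that Section III.C states one goal for both arms, 2 or more twitches, and ties the 2 mg/kg sugammadex dose to the second twitch. If that goal is followed, s = 0 and the arms share one start rule. This stands. The mechanism is possible under the table, but nothing shows that it will operate.

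A reader might infer that waiting is dropped from the neostigmine arm alone. The documents do not say so: a sugammadex patient may also wait, and that wait is uncounted too. What differs is that waiting is compulsory in one arm and optional in the other.

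A reader might also infer that slow sugammadex recovery from deep block will be set against fast neostigmine recovery from shallow block. No figure supports this. The table gives a larger sugammadex dose at deep block, and Section II says only that neostigmine is slower and less effective overall.

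Time from administration is, further, a coherent measure of drug speed, and no stated objective concerns waiting. This stands as well, and is why the measure should be kept. It does not make the start depths comparable or visible.

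Finally, total operating room time includes any wait in both arms. That is true, but it covers the whole transplant, so a few minutes are easily lost in it. The outcomes are additional, and any distortion would work against the intervention. That limits what is at stake without making the comparison interpretable.

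**Conclusion.** The concern holds in a limited form. Both speed outcomes start at a moment after randomisation whose timing rule differs by arm for patients with fewer than 2 twitches. The clock can then start at different depths, and waiting can be left out unequally. This could understate a difference in favour of sugammadex.

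The size is unknown. It averages 0-8 min per patient if 10-40% are affected, the wait is 10-20 min and 0-100% of affected sugammadex patients are dosed at once. All three ranges are assumptions. It is exactly 0 if the 2-twitch goal is followed in both arms, and patients reversed at 2 or more twitches contribute nothing to it.

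It would go too far to conclude that the comparison is biased as planned: that needs deeply blocked patients and early sugammadex dosing, and the documents establish neither. The primary outcome does not use these times and is untouched.

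**What to change.** 1. In both arms, also record and compare the time from one fixed, objectively defined end-of-surgery time stamp (for example skin closure) to T4/T1 above 0.9 and to extubation. The primary outcome already runs from the end of surgery, but the plan does not define that as a time stamp. State how the times will be compared, since Statistical Methods is silent on them.
2. Record the twitch count at dosing and report time from administration alongside it. This is description rather than a repair by adjustment, because depth at dosing can itself depend on the arm.
3. Reconcile the text and the table in Section III.C on when sugammadex is given. This review takes no view on which is right.

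The cost is a few lines of wording, one time stamp from the anaesthesia record and one twitch count per patient. The downside is that the new interval includes any delay in giving the drug, and an unblinded investigator controls that delay. It should therefore be presented as a measure of the whole reversal strategy, next to time from administration and not in place of it. If the 2-twitch goal is always met, the added data will show that at little cost.

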The secondary analysis comparing delayed efficacy of sugammadex to neostigmine in reducing the incidence of hypoventilation during the first 3 postoperative days will assume the same model and covariates as the primary hypothesis. To compare the incidence of PPCs a logistic regression model will be used with the binary outcome of any PPC and will include covariates for group and total morphine equivalents. Hospital length of stay and costs will be compared between groups using a linear regression model including covariates for group, total morphine equivalents, presence of respiratory comorbidities and other clinical differences that may influence the outcome. Continuous outcomes may be transformed if they violate the normality assumption (e.g., a log-transformation).

Multiplicity

Given only one primary outcome and hypothesis, there is a not a concern for multiplicity. Secondary analyses are considered exploratory in this protocol.

Power/Sample Size:

Based upon a sample size of 40 patients per group, this study has 90% power to detect a 50% difference in hypoventilation incidence in the PACU (from 76% as reported in previous studies[21] to 38%, alpha 0.05), assuming a potential dropout of up to 6 patients per group. The 50% reduction is considered clinically relevant for a decrease in the frequency of hypoventilation, a precursor of more clinically significant complications such as hypoxemia, reintubation or pneumonia. Quantifying the contribution of hypoventilation into more severe complications is challenging, and details of duration and severity of hypoventilation are not well known. Thus, only a significant reduction in hypoventilation incidence (i.e. 50%) may be accepted as relevant. This trial will provide additional detailed information that may provide more insight on the clinical consequences of hypoventilation (e.g. potential association between accumulated minutes of MV <40% expMV and decrease in SpO₂/FiO₂ over the following 30 min).

A sample size of 40 patients per group would also have approximately 80% power (78%) to detect a difference in case the incidence of any hypoventilation events is 60%, instead of the literature-based 76%. The table below provides the sample size per group to achieve a variety of assumptions for the primary outcome, alpha, and power:

Incidence Group 1	Incidence Group 2	Alpha	Power	Sample Size per Group
1. 0.76	2. 0.38	3. 0.01	4. 0.8	5. 39
6. 0.76	7. 0.38	8. 0.05	9. 0.8	10. 26

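### The unplanned-intubation item of the PPC list excludes everyone who leaves the operating room intubated, including patients left intubated because reversal failed

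*Combined protocol and SAP*

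**What the plan says.** Section III.F, Variables/Time Points of Interest, introduces the list as "Postoperative Pulmonary Complications (PPCs) following previous definitions[13, 41, 42], including" and then defines eight items: respiratory failure, unplanned intubation, ARDS, pneumonia, pneumothorax, atelectasis, pleural effusion and bronchospasm. The second item reads "Unplanned intubation with postoperative mechanical ventilation (POMV), defined as placement of a breathing tube that was not intended or planned". It leaves out intubation during an unplanned return to surgery and then adds "Also excluded those patients that were transferred intubated and ventilated to the intensive care unit (ICU) from the operating room". No reason for leaving intubated is asked for, and none is exempt.

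Three other places bear on this:

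- Section III.C, Preoperative phase, on timing: "Randomization will occur after patients consent for the study". Allocation therefore comes before surgery, reversal and extubation.
- Section III.C, Intraoperative phase: "Extubation will be performed following the usual standard of care criteria", to which the protocol adds a quantitative T4/T1 above 0.9.
- Section III.F, Statistical Methods: "To compare the incidence of PPCs a logistic regression model will be used with the binary outcome of any PPC". The Multiplicity paragraph adds "Secondary analyses are considered exploratory in this protocol".

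**The concern.** The trial compares two drugs whose effect helps decide whether a patient can be extubated. If reversal is inadequate and the T4/T1 threshold is not reached, the patient may leave the operating room with the tube in place. The unplanned-intubation item then cannot register that patient. A patient who is extubated and later reintubated for the same weakness can be registered. The exclusion thus depends on an event that follows randomisation and that treatment can influence.

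The plan's own premise is that such events may be uneven. The Background describes neostigmine as slower and less effective at reversal. If more patients in one arm leave intubated for that reason, the rule flatters that arm. This touches a stated secondary objective (section I, Objectives), which concerns pulmonary complications that may stem from inadequate reversal.

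**Working it through.** **Is there a figure to reproduce?** Not for PPCs. The documents give no PPC rate and no rate of leaving the room intubated. The only planned numbers are for the primary outcome: 76% vs 38%, alpha 0.05 and 90% power need 34 per group. A two-sided pooled-variance calculation without continuity correction also gives 34. Adding up to 6 dropouts gives 34 + 6 = 40 per group. That figure serves here only as a denominator.

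**Can such a patient count elsewhere in the list?** The other seven items carry no matching exclusion, but each needs its own finding:

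- Respiratory failure and ARDS need impaired oxygenation. The former includes "a ratio of PaO_2 to inspired oxygen fraction < 300 or arterial oxyhemoglobin saturation measured with pulse oximetry" among its criteria, so a ventilated patient with poor gas exchange does count.
- Pneumonia, pneumothorax, atelectasis and pleural effusion need imaging or clinical findings. The plan orders no tests for the study.
- Bronchospasm needs a chart entry plus bronchodilator use.

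A patient ventilated purely for weakness, with good oxygenation and clear imaging, can meet none of the seven.

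**What is one patient worth?** One patient is 1/40 = 2.5 points at 40 per arm, or 1/34 = 2.9 points at 34. For any PPC the effect depends on two things: whether the patient meets another item, and whether excluded means scored as a non-event or dropped from the denominator. The text does not settle the second.

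**Illustration, on assumed figures.** Suppose 8 of 40 patients (20%) in each arm have a PPC for other reasons. Suppose also that k neostigmine patients leave intubated and meet no other item. The neostigmine any-PPC rate is then:

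| k | Counted as event, (8+k)/40 | Non-event, 8/40 | Dropped, 8/(40−k) |
|---|---|---|---|
| 1 | 22.5% | 20.0% | 20.5% |
| 2 | 25.0% | 20.0% | 21.1% |
| 4 | 30.0% | 20.0% | 22.2% |

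With sugammadex at 20.0%, counting these patients shows a difference of k/40: 2.5, 5.0 and 10.0 points. Scoring them as non-events shows none. Dropping them shows 0.5, 1.1 and 2.2 points, so it hides 22.5 − 20.5 = 2.0, 25.0 − 21.1 = 3.9 and 30.0 − 22.2 = 7.8 points. If every such patient meets another item and stays in the denominator, nothing is hidden. Neither k nor the 20% comes from the documents.

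**The case against.** The case against is substantial.

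- **It is one item of eight.** A reader might infer that these patients are removed from the PPC outcome or from the trial. No text says so. The sentence limits what counts as an unplanned intubation, and the analysis uses any PPC. This stands.
- **The item measures placement of a tube.** A patient never extubated has had no new tube placed, so the limit is coherent as a definition. This stands as a reading of the item. It is also why a separately listed item is an acceptable remedy. It does not answer the point that no item counts failure to extubate as such.
- **Other outcomes record the same course.** A reader might infer that the trial hides its worst reversal failures. It does not: time to T4/T1 >0.9, time to extubation, total operating room time, ICU admission and ICU stay are all listed. They do not feed into any PPC, however, and ICU admission is recorded without a stated reason.
- **The causal chain is possible, not established.** Slow reversal may simply prolong operating room time, since the dosing table allows waiting. Patients may also stay intubated because of consciousness or airway-reflex criteria. Calling the excluded patients the most severe failures, or expecting a particular imbalance between arms, goes beyond the documents.
- **Provenance.** A reader might suppose the definition was built for settings where treatment did not determine extubation. The documents do not describe those settings, so nothing rests on that here.
- **A reason-based event invites judgement.** The intraoperative phase is run by the unblinded investigator. This stands, and the remedy should use an objective marker instead.

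**Conclusion.** The concern holds in a limited form. Within one secondary, exploratory item, the plan excludes patients on the basis of a post-randomisation event that the assigned drug can cause. That can bias the item, and possibly any PPC, in favour of the arm with more reversal failures. The size cannot be derived from the documents. At 40 per arm, each affected patient is worth from 0 points of any PPC (another item is met and the patient stays in the denominator) to 2.5 points (no other item is met and the patient is scored as a non-event).

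The point is minor. Section III.E already concedes that the sample may be too small for clinical complications. A reader might infer that the primary result is affected, but this sentence does not alter the primary outcome's definition. How a patient sent directly to the ICU is classified for the primary outcome, whose monitoring starts on PACU arrival, is a separate question that the plan leaves open.

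**What to change.** In section III.F:

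1. Limit the exclusion to patients whose postoperative ventilation was documented as planned before the reversal drug was given.
2. Count any other patient who leaves the operating room intubated as an event, either in this item or as a separately listed PPC item.
3. Report the last recorded T4/T1 for these patients as the objective marker of reversal failure, rather than relying on a reason given by the unblinded investigator. The plan already repeats the measurement every 30 seconds after reversal.
4. State that all randomised patients stay in the any-PPC denominator.
5. Report the number leaving intubated by arm.

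The cost is a short text change and one extra data field. Some patients left intubated for reasons unrelated to reversal will be counted, and the rate becomes slightly less comparable with sources using the cited definitions. Only the classification of the endpoint changes. Clinical management does not.
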